2.1 Primary endpoints

The primary endpoints are the person-time incidence rates of each of the following:

- Adverse events (AEs) leading to premature study discontinuation.
- Thromboembolic events (TEEs).
- Anaphylaxis.
- HAE attacks resulting in in-patient hospitalization.
- Solicited AEs (injection site reactions at the CSL830 injection site) graded as severe by the investigator.
- Related serious AEs (SAEs), other than events specified above.
- Anti-C1-esterase inhibitor (C1-INH) antibodies (inhibitory or non-inhibitory).

For each primary endpoint safety event, the person-time incidence rates are calculated as:

- the number of subjects experiencing the primary endpoint safety event at least once during treatment with CSL830, divided by the sum of each subject's time at risk

and

- the total number of the primary endpoint safety events divided by the sum of each subject's time at risk.

Further details how the number of subjects experiencing the primary endpoint safety event, the number of the primary endpoint safety events and the time at risk will be calculated are outlined in [Section 4.7.1](#).

2.2 Secondary endpoints

2.2.1 Secondary safety endpoints

The secondary safety endpoints are the following:

- AEs,
- Solicited AEs,
- Unsolicited AEs,
- SAEs,
- Temporally-related AEs (AEs which start within 24 hours of administration of the investigational product),
- Suspected adverse drug reactions (ADRs) (AEs which start within 24 hours of administration of the investigational product or which are related to investigational product administration including AEs with missing causality rating),
- The CSL830 injections followed by at least one solicited AE,
- Subjects reporting CSL830 injections followed by at least one solicited AE,
- Risk scores for deep vein thrombosis (DVT) or pulmonary embolism (PE),
- TEEs,
- Hypersensitivity,
- Anaphylaxis,
- Clinical laboratory assessments:
 - Hematology.
 - Biochemistry.
 - Urinalysis.
 - Coagulation profile.
 - Anti-C1-INH antibodies.
 - Viral serology.
- Vital signs including body weight,
- Physical examination.

2.2.2 Secondary efficacy endpoints

Efficacy endpoints considered as secondary include the following:

- The percentage of subjects who are responders. “Response” is defined as a $\geq 50\%$ relative reduction in the time-normalized number of HAE attacks during treatment with CSL830, compared with the time-normalized number of attacks that is used to qualify the subject for participation in this study (see Section 4.1.2 of the protocol [inclusion criterion 5]).
- The percentage of subjects who experience a time-normalized HAE attack frequency of < 1 HAE attack per 4-week period.

2.3 CCI [redacted]

2.2.3 CCI [redacted]

CCI [redacted]

CCI [redacted]

CCI [redacted]

[redacted]

[redacted]

[redacted]

[redacted]

[redacted]

[redacted]

[redacted]

[redacted]

[redacted]

[redacted]

[redacted]

[redacted]

[redacted]

[redacted]

[redacted]

[redacted]

CCI
[Redacted text block]

CCI
[Redacted text block]

CCI
[Redacted text block]

[figure not shown]
3 Study Design

3.1 Discussion of Study Design

3.1.1 Study Design

This is a multicenter, randomized, open-label, parallel-arm, phase 3b study designed to investigate the safety and efficacy of SC administered CSL830 in the prophylactic treatment of HAE. An overview of the study is depicted in Figure 1.

Figure 1: Study Overview

Footnotes to Figure 1:

^a “CSL830-Interrupted” Subjects and “CSL830-Naïve” Subjects will participate in a Screening Visit in order to confirm their eligibility. “CSL830-Continuation” Subjects will not be required to participate in a Screening Visit. Instead, data from study CSL830_3001 will be used to confirm their eligibility (see Section 8.4.3.1).

NOTE: The definitions for “CSL830-Continuation” Subjects, “CSL830-Interrupted” Subjects, and “CSL830-Naïve” Subjects are presented in Section 4.1.1 of the Protocol.

^b During the fixed-dose Treatment Period 1, subjects who experience very frequent HAE attacks (ie, ≥ 12 attacks, as defined per protocol, within a 4-week evaluation period) are eligible for CSL830 dose increases in increments of 20 IU/kg (up to a maximum dose of 80 IU/kg). All CSL830 dose increases are optional, and will be made only in subjects who are eligible, at the sole discretion of investigator. An evaluation period for any dose increase is defined as beginning after a dose-stable period (ie, 2 weeks after the initiation or dose increase of CSL830). See Section 3.2 of the Protocol for additional details.

^c Beginning with the Week 25 Visit and throughout Treatment Period 2, subjects who experience ≥ 3 HAE attacks (as determined per protocol) within an 8-week evaluation period are eligible for CSL830 dose increases in increments of 20 IU/kg (up to a maximum dose of 80 IU/kg). All CSL830 dose increases are optional, and will be made only in subjects who are eligible, at the sole discretion of investigator. An evaluation period for any dose increase is defined as beginning after a dose-stable period (ie, 2 weeks after the initiation or dose increase of CSL830). See Section 3.2 of the Protocol for additional details.

^d For subjects (from the United States) enrolled in the Extension Period, their CSL830 dose will be escalated in increments of 20 IU/kg (up to a maximum dose of 80 IU/kg) according to the rules outlined for Treatment Period 2 (see Section 3.2), but their CSL830 by-weight dose will be rounded to the nearest (ie, up *or* down) 1000 IU based on their assigned dose for subjects weighing ≥ 40 kg; subjects weighing < 40 kg will continue to undergo rounding as during Treatment Periods 1 and 2 (ie, rounded up to the nearest 500 IU).

^e Subjects will undergo a 2-week (± 3 days) follow-up contact after either completing or discontinuing/withdrawing from the Extension Period.

3.1.2 Screening Visit

A Screening Visit will be conducted within the 4 weeks before Treatment Period 1 in order to confirm the eligibility of the following subjects:

- “CSL830-Naïve” Subjects: subjects who did not participate in study CSL830_3001; subjects who participated in study CSL830_3001 but did not receive blinded investigational product as a part of that study.
- “CSL830-Interrupted” Subjects: subjects who completed participation in study CSL830_3001, but who delayed entry into the current study (ie, > 1 week between the End of Study Visit of CSL830_3001 and the first visit of CSL830_3002 Treatment Period 1).

The first visit in Treatment Period 1 (i.e., the Day 1 Visit) may occur on the same day as the Screening Visit but after the End of Study Visit of CSL830_3001.

“CSL830-Continuation” Subjects will not have a Screening Visit. “CSL830-Continuation” Subjects are subjects who complete participation in CSL830_3001 and who continue directly on to participate in the current study [i.e., ≤ 1 week between the End of Study Visit of CSL830_3001 and the first visit of CSL830_3002 Treatment Period 1].

The eligibility of “CSL830-Continuation” Subjects will include evaluation based upon the assessments performed during study CSL830_3001 as described in Table 6 of the protocol (Section 8.4.3.1). For “CSL830-Continuation” Subjects, the End of Study Visit of CSL830_3001 and the first study visit of Treatment Period 1 of CSL830_3002 may occur on the same day.

3.1.3 Treatment Periods 1 and 2

Treatment Period 1 will begin with the Day 1 Visit and will end with the Week 25 Visit, i.e. last until (excluding) the Week 25 Visit. Treatment Period 2 will begin immediately with the Week 25 Visit. Treatment Period 2 will end with completion of the Week 53 Visit (last visit of Treatment Period 2). Subjects will attend a Follow-up Visit occurring 14 days (\pm 3 days) after the final visit in Treatment Period 2 or any visit resulting in study discontinuation, unless informed consent/assent has been withdrawn.

Eligible subjects will be randomized to 1 of the following CSL830 treatment groups at the first visit in Treatment Period 1:

- 40 IU/kg CSL830 treatment group, or
- 60 IU/kg CSL830 treatment group.

CSL830 will be administered as a single SC injection twice weekly at home either independently (i.e., self-administered by the subject) or with assistance (i.e., with the help of a caretaker such as a parent or guardian) during Treatment Period 1 and Treatment Period 2.

During the study, an investigator may increase a subject’s CSL830 dose if that subject is eligible for dose increase. A subject’s eligibility for a dose increase is related to the frequency of his or her HAE attacks. The rules for a dose increase are different during the “fixed dose” Treatment Period 1 and the “dose optimization” Treatment Period 2.

Dose increase rules are presented in [Section 3.2](#).

3.1.4 Extension Period

The Extension Period is intended to allow subjects from the United States who complete Treatment Period 2 according to the protocol to continue to receive treatment with open-label CSL830.

The Extension Period will follow Treatment Period 2. The last visit (Week 53 Visit) of Treatment Period 2 will serve as the first visit of the Extension Period (Extension Period Week 0, Extension Period Day 1), unless there is a rest period of up to 30 days. In this case, the first visit of the Extension Period will be a new (separate) visit. If the last visit of Treatment Period 2 and the first visit of the Extension Period are more than 14 days apart, subjects will attend a Follow-up Visit occurring 14 days (\pm 3 days) after the final visit in Treatment Period 2. The Extension Period will start with Extension Period Week 0 and will end with the Extension Period Week 88 Visit. Subjects will attend a Follow-up Visit (phone call) occurring 14 days (\pm 3 days) after the final visit in the Extension Period or any visit resulting in study discontinuation, unless informed consent/assent has been withdrawn.

Of note, only AEs, HAE attacks and medications will be captured in the eDiary for the rest period. It will also be entered that there was no study treatment.

3.1.5 Planned number of sites

The study is planned to be conducted at approximately 50 study sites.

3.2 Study Treatment

The doses of CSL830 (40 IU/kg and 60 IU/kg) to be assessed in the current study were selected based on the results of the CSL830_2001 study.

A subject will be randomized to one of 2 treatment groups (CSL830 40 IU/kg or CSL830 60 IU/kg) and will administer CSL830 via a single SC injection, twice weekly. 40 IU/kg CSL830 is equivalent to a volume of 0.08 mL/kg; 60 IU/kg CSL830 is equivalent to a volume of 0.12 mL/kg. The volume to be administered (planned volume) is based on treatment assignment, a subject's baseline body weight (Day 1, Treatment Period 1), and rounding (i.e., up to the nearest whole mL). For those subjects who experienced a body weight change of more than 10% relative to baseline, the dose is to be adjusted and subsequent weight measurements are to be compared to the new weight. For those subjects who experience a body weight change of more than 10% relative to the new weight, the dose is to be adjusted again. This is repeated throughout the study. To promote compliance, the twice weekly administration of CSL830 should be scheduled on fixed days of the week (e.g., Monday and Thursday). The suggested interval between each administration of CSL830 is 3 or 4 days. In addition, CSL830 should be administered at approximately the same time on each day. A missed injection should be administered as soon as possible, unless within 24 hours of the next scheduled injection; in this situation, the missed injection should be omitted, and the administration of CSL830 should occur at the next scheduled day and time.

Beyond the Week 53 Visit, the volume to be administered (planned volume) is based on treatment assignment, a subject's body weight, and rounding (i.e., the actual dose of CSL830 that is assigned will be rounded (i.e., up or down) to the nearest 1000 IU for subjects

weighing ≥ 40 kg; subjects weighing < 40 kg will continue to undergo rounding as during Treatment Periods 1 and 2 (i.e., rounded up to the nearest 500 IU, for further details please see Country-Specific Protocol Amendment No. 1 (United States), dated 10 July 2015).

If a subject requires the use of C1-INH medication for the treatment of HAE attacks within 24 hours before a scheduled injection of CSL830, the scheduled injection may be delayed by up to 24 hours.

CSL830 Dose Increase

Some subjects may be eligible to increase the dose of CSL830 to which they were randomized at the beginning of Treatment Period 1.

During the fixed-dose Treatment Period 1, subjects who experience very frequent HAE attacks (i.e., ≥ 12 attacks, as defined per protocol, within a 4-week evaluation period) are eligible for CSL830 dose increases in increments of 20 IU/kg (up to a maximum dose of 80 IU/kg). All CSL830 dose increases are optional, and will be made only in subjects who are eligible for a CSL830 dose increase, at the sole discretion of investigator. Dose increases during Treatment Period 1 are intended as rescue prophylaxis, to provide the opportunity for subjects who have very frequent HAE attacks to continue in the study during this otherwise fixed-dose treatment period.

Beginning with the Week 25 Visit and throughout Treatment Period 2, subjects who experience ≥ 3 HAE attacks (as determined per protocol) within an 8-week evaluation period are eligible for CSL830 dose increases in increments of 20 IU/kg (up to a maximum dose of 80 IU/kg). All CSL830 dose increases are optional, and will be made only in subjects who are eligible for a CSL830 dose increase, at the sole discretion of investigator. Dose increases during Treatment Period 2 are intended to allow investigators to adjust/optimize the dose for subjects who may need a higher prophylactic dose.

During the Extension Period, each subject will continue to be eligible for dose escalation in increments of 20 IU/kg (up to a maximum dose of 80 IU/kg) according to the rules outlined for Treatment Period 2.

An evaluation period for any dose increase in either Treatment Period 1, Treatment Period 2, or the Extension Period will start after a dose-stable period which is defined:

- In Treatment Period 1 as the 2 weeks after the start of a CSL830 dose or a dose increase
- In Treatment Period 2 as the 2 weeks after a subject has a dose increase
- In the Extension Period as the 2 weeks after a subject has a dose increase or after a rest period prior to the Extension Period.

The evaluation period for a dose increase has no relevance for any statistical analyses.

CSL830 dose increases will be made in increments of 20 IU/kg up to a maximum dose of 80 IU/kg. Subjects who are randomized to treatment with 40 IU/kg CSL830 and who are eligible for a dose increase may undergo up to 2 independent 20 IU/kg dose increases (at the sole discretion of the investigator), up to a maximum dose of 80 IU/kg. Subjects who are randomized to treatment with 60 IU/kg CSL830 and who are eligible for a dose increase may undergo a single 20 IU/kg dose increase (at the sole discretion of the investigator), up to a maximum dose of 80 IU/kg.

3.3 Study Schedule

3.3.1 Planned study duration

The duration of the study for an individual subject who does not participate in the Extension Period is expected to be up to 58 weeks. This estimation is based on:

- A Screening Period lasting up to 4 weeks (≤ 28 days), as needed.
- Two treatment periods totaling 52 weeks (367 days \pm 2 days).
- A Follow-up Period lasting 2 weeks (14 days \pm 3 days).

The overall study duration (i.e., from the first subject's first Screening Visit to the last subject's Follow-up Visit) is planned to be 26 months, but will depend on recruitment.

US-subjects will have the opportunity beyond the Week 53 Visit to enter into an Extension Period of up to 90 weeks. The Extension Period will comprise a treatment period of 88 weeks and a follow-up period of 14 days \pm 3 days (see Country-Specific Protocol Amendment No. 1 (United States), dated 10 July 2015).

3.3.2 Screening

The eligibility of "CSL830-Naïve" Subjects and "CSL830-Interrupted" Subjects will be assessed at a Screening Visit conducted within the 4 weeks before Treatment Period 1.

The Screening Visit and the Day 1 Visit of Treatment Period 1 can occur on the same day. If a subject fails Screening at a combined Screening Visit / Day 1 Visit, then the subject will be treated as a screen failure.

For "CSL830-Naïve" Subjects and for "CSL830-Interrupted" Subjects, the first study visit of study CSL830_3002 is the Screening Visit of study CSL830_3002.

If a potential subject was not entered into Treatment Period 1 of the current study within the 4 weeks following the Screening Visit, the potential subject may attend a second Screening Visit (for a maximum of 2 Screening Visits per subject). In the event that a potential subject is screened twice, all Screening Period assessments including medical history must be repeated at the second Screening Visit and these finding / results will supersede those from the previous Screening Visit. CCI

3.3.3 Schedule of Events

See Section 8 "Study Procedures and Visit Schedule" of the Country-Specific Protocol Amendment No. 1 (United States) for details of the schedule of procedures and assessments during the extension period.

3.3.4 Unscheduled Visits

Unscheduled visits can be arranged at any time point during the study (e.g., to reinstruct subject on correct injection technique, dosing regimen, or use of eDiary; to repeat a study procedure; to pick up new study medication), at the discretion of the investigator or upon request of the subject.

Measurements from unscheduled visits will be listed but not included in summary tables.

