2.2.2 Secondary Endpoints

1. The secondary safety endpoints are the following:
 - a. The percentage of subjects experiencing the following events: SAEs, temporally-related AEs, increased risk scores for DVT or PE, TEEs, inhibitory anti-C1-INH antibodies, or clinically significant abnormalities in laboratory assessments (ie, lab abnormalities reported as AEs).
 - b. The percentage of administrations of CSL830 resulting in solicited local AEs (discomfort [eg, pain, burning], swelling, bruising, or itching at the CSL830 injection site).
 - c. The percentage of subjects who have at least 1 solicited local AE (discomfort [eg, pain, burning], swelling, bruising, or itching at the CSL830 injection site).
 - d. The percentage of subjects who become seropositive for HIV-1/-2, HBV, or HCV.

The secondary safety endpoints will be assessed for Treatment Period 1, Treatment Period 2 and Treatment Periods 1 and 2 (together). The secondary safety endpoints will also be assessed for the Extension Period (only) and for the treatment periods overall for subjects who are included in the Extension Period.

2. Efficacy endpoints considered as secondary include the following:
 - a. The percentage of subjects who experience a time-normalized HAE attack frequency of < 1 HAE attack per 4-week period.
 - b. The percentage of subjects who are responders. “Response” is defined as a $\geq 50\%$ relative reduction in the time-normalized number of HAE attacks during treatment with CSL830, compared with the time-normalized number of attacks that is used to qualify the subject for participation in this study (see [Section 4.1.2](#) [inclusion criterion 5]).

The secondary efficacy endpoints will be assessed for Treatment Period 1, and Treatment Periods 1 and 2 (together). The secondary efficacy endpoints will also be assessed for the Extension Period (only) and for the treatment periods overall for subjects who are included in the Extension Period.

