10.3 Safety Assessments

Safety will be assessed using:

- Vital signs.
- Physical examination.
- Clinical scores of risk assessment for DVT and PE.
- Solicited local AEs (ie, injection site reactions).
- Other AEs, including SAEs.
- Clinical laboratory assessments:
 - Hematology.
 - Biochemistry.
 - Coagulation profile
 - Viral serology.
 - Anti-C1-INH antibodies.
 - Urinalysis.

Clinical laboratory tests will be performed at time points as detailed in the schedule of assessments (the [Schedule of Laboratory Assessments for “CSL830-Continuation” Subjects](#), the [Schedule of Laboratory Assessments for “CSL830-Interrupted” Subjects and “CSL830-Naïve” Subjects](#), and the [Schedule of Events for the Extension Period](#)). More frequent evaluations may be performed, if clinically indicated, at the discretion of the investigator. The laboratory values will be entered into the eCRF using the same units as provided by the laboratory. Verification of the laboratory values, if applicable, will be recorded in the source data.

All abnormal laboratory values will require a comment by the investigator on the respective eCRF or the laboratory report. The following codes should be used:

- Error (ER) (eg, laboratory error, improper sample preparation, hemolysis, delayed transit to laboratory).
- Abnormal, not clinically significant (ANCS).

- Abnormal, clinically significant (ACS).

Tests resulting in abnormal laboratory values during the study period that have been classified by the investigator as ACS should be repeated as soon as possible after receiving the laboratory report to rule out laboratory error.

Any laboratory values that deviate from the reference ranges and are considered by the investigator as clinically significant (ie, classified as an ACS value) at any visit after baseline also must be documented in the eCRF as an AE.

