4.7.2.3 Analysis of Laboratory Findings

Normal ranges will be provided for laboratory tests. Values outside the normal range will be judged as clinically significant or non-clinically significant by the investigator. All abnormal laboratory data considered as clinically significant will be presented as AE.

All continuous laboratory parameters will be plotted against their scheduled assessments visits.

Analyses of haematology, biochemistry, and coagulation parameters will consist of the following:

- Descriptive statistics for baseline and each treatment visit, including changes from baseline to each treatment visit
- Mean values and the SD of the continuous laboratory parameters at each scheduled visit will be plotted against scheduled visits.

Baseline will be the assessment before the first injection (Week 1 Day 1) for all “CSL830-Naïve” and “CSL830-Interrupted” Subjects and “CSL830-Continuation” Subjects who did not complete the assessments at the CSL830_3001 End of Study Visit. For “CSL830-Continuation” Subjects who complete the assessments at the CSL830_3001 End of Study Visit, these assessments will be the baseline. If the baseline value for a subject is missing, no change from baseline will be calculated for the subject.

The number and percentage of subjects without anti-C1-INH antibodies and with anti-C1-INH antibodies (inhibitory, non-inhibitory and inhibitory and non-inhibitory combined) during the study will be summarized overall and for each study visit

Urinalysis, viral serology and pregnancy testing results will be listed only.

Notes:

- All results outside predefined normal ranges will be flagged as high or low in the data listings.
- Clinically significant laboratory values will be flagged in the listings.
- Unscheduled results will be listed only and not included in summary tables.

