4.7.5 Risk Assessment for Deep Vein Thrombosis and Pulmonary Embolism

The clinical model scoring system will be used for the risk assessment of deep vein thrombosis:

Clinical Feature	Score
Active cancer (treatment ongoing or within previous 6 months or palliative)	+1
Paralysis, paresis, or recent plaster immobilization of the lower extremities	+1
Recently bedridden for more than 3 days or major surgery, within 4 weeks	+1
Localized tenderness along the distribution of the deep venous system	+1
Entire leg swollen	+1
Calf swelling by more than 3 cm when compared with the asymptomatic leg (measured 10 cm below tibial tuberosity)	+1
Pitting edema (greater in the symptomatic leg)	+1
Collateral superficial veins (non-varicose)	+1
Alternative diagnosis as likely or greater than that of deep vein thrombosis	-2

Note: In subjects with symptoms in both legs, the more symptomatic leg is used.

Individual clinical feature scores and calculated risk scores will be recorded in the eCRF.

If a subject has a risk score of ≥ 1 , a lower extremity ultrasound examination will be arranged by the investigator to exclude deep vein thrombosis. If a deep vein thrombosis is confirmed on ultrasound examination, the event will be classified as an AESI and will be reported as a SAE.

The following clinical model scoring system will be used for the risk assessment of pulmonary embolism:

Clinical Feature	Score
Previous pulmonary embolism or deep vein thrombosis	+1.5
Heart rate >100 beats per minute	+1.5
Immobilization or surgery in the previous four weeks	+1.5
Clinical signs and symptoms of deep vein thrombosis (minimum of leg swelling and pain with palpation of the deep veins)	+3
Alternative diagnosis less likely than pulmonary embolism	+3
Hemoptysis	+1
Malignancy (on treatment, treated within the last 6 months, or palliative)	+1

Individual clinical feature scores and calculated risk scores will be recorded in the eCRF.

If a subject has a risk score of ≥ 2 , a computerized tomographic (CT) angiogram or appropriate investigation will be arranged by the investigator to exclude pulmonary embolism. If pulmonary embolism is confirmed on investigation, the event will be classified as an AESI and will be reported as a SAE.

The number and percentage of subjects with a risk score for deep vein thrombosis and pulmonary embolism of ≥ 1 or ≥ 2 (respectively) will be summarized at each visit.

CCI [REDACTED]

CCI [REDACTED]

[REDACTED]

[REDACTED]

[REDACTED]

[REDACTED]

[REDACTED]

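### The blanket exclusion of unscheduled results can drop antibody positives from the overall antibody table, and the SAP does not say whether they count in the primary antibody rate

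*SAP*

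**What the plan says.** - **General rule.** SAP 3.3.4: "Measurements from unscheduled visits will be listed but not included in summary tables".
- **Laboratory rule.** SAP 4.7.2.3, in the notes that close the section: "Unscheduled results will be listed only and not included in summary tables". Neither place makes an exception for any type of table.
- **Antibody table.** The same section 4.7.2.3 says that the numbers of subjects with and without anti-C1-INH antibodies "during the study will be summarized overall and for each study visit".
- **Primary endpoint.** SAP 2.1 makes anti-C1-INH antibodies, inhibitory or not, a primary endpoint. The subject-based rate takes as its numerator "the number of subjects experiencing the primary endpoint safety event at least once during treatment with CSL830". SAP 4.7.1 sets out the numerators, the time at risk and the confidence interval, and does not mention unscheduled samples.
- **Extra testing.** Protocol 10.3, which lists these antibodies among the clinical laboratory assessments: "More frequent evaluations may be performed, if clinically indicated, at the discretion of the investigator". Protocol 8.4.7 names repeating a study procedure as one reason for an unscheduled visit.
- **DVT/PE scores.** SAP 4.7.5 tabulates how many subjects reach the threshold, by visit only: "risk score for deep vein thrombosis and pulmonary embolism of ≥ 1 or ≥ 2 (respectively) will be summarized at each visit". Protocol 2.2.2 instead counts subjects experiencing, among other events, "increased risk scores for DVT or PE, TEEs, inhibitory anti-C1-INH antibodies, or clinically significant abnormalities in laboratory assessments", by treatment period.

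**The concern.** Leaving unscheduled values out of a by-visit table is normal practice, because such values belong to no scheduled column. A count of subjects who were ever positive has no columns to protect, and there the same rule produces a wrong count. Here it is worded to cover both kinds of table.

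Antibody status is exposed to this because scheduled sampling is sparse. A sample taken between visits because something prompted it may be the only positive a subject has. If it is listed and nothing more, the whole-study table shows fewer positive subjects than the database holds. For the primary rate, the programmer has a rule that says unscheduled results are listed only, and no instruction in 4.7.1 to the contrary. At stake are the count behind one of seven primary endpoints, and the date and dose to which an antibody event is attributed.

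**Working it through.** **1. The plan's own figure.** The only design calculation is 100 subjects, 3%, 95% confidence (SAP 3.8). It reproduces: 1 − 0.97^100 = 0.952. The point does not depend on it.

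**2. The literal reading.** Take a subject with negative scheduled samples and one positive unscheduled sample.
- By-visit antibody table: left out of the visit columns, as is usual.
- Overall antibody table: 4.7.2.3 requires this table and, a few lines later, bars unscheduled results from summary tables. The subject appears as having no antibodies.
- Primary antibody rate: positive at least once during treatment under 2.1, but listed only under 3.3.4 and 4.7.2.3. Section 4.7.1 does not settle which governs.

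**3. Sampling gaps.** The protocol schedules give Day 1, Week 25 and Week 53; sections 8.4.6.6 to 8.4.6.22 give Extension Weeks 24, 48, 72 and 88. Nominal gaps are 24 and 28 weeks, then 24, 24, 24 and 16 weeks, ignoring visit windows and any rest period.

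**4. Effect of an omitted subject (illustration).** The number of unscheduled positives is not in the documents; I assume 0 to 3. Exposure is also assumed:
- Treatment Periods 1 and 2, 100 completers for 366 days: T = 100 × 366/365.25 = 100.2 years.
- With the Extension Period pooled, as SAP 4.1 and 4.14 plan, 110 subjects for 366 days and 50 for 88 weeks (616 days), no dropout: T = 110 × 366/365.25 + 50 × 616/365.25 = 110.23 + 84.33 ≈ 194.6 years.

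The interval is that of SAP 4.7.1 with k = 1: lower = χ²(2Y, 0.025)/(2T), upper = χ²(2Y + 2, 0.975)/(2T), with lower set to 0 when Y = 0. Follow-up weeks and the shortening of time at risk after a first event are ignored.

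| Positive subjects Y | Rate per year (95% CI), T = 100.2 | Rate per year (95% CI), T = 194.6 |
|---|---|---|
| 0 | 0 (0 to 0.0368) | 0 (0 to 0.0190) |
| 1 | 0.0100 (0.0003 to 0.0556) | 0.0051 (0.0001 to 0.0286) |
| 3 | 0.0299 (0.0062 to 0.0875) | 0.0154 (0.0032 to 0.0451) |

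As a percentage, each omitted subject costs 1/110 = 0.9 points.

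Zero against one is not the likeliest case for the endpoint as a whole. Protocol 1.4 reports antibodies in 7 of 18 subjects (39%) in CSL830_2001. At that proportion about 43 of 110 would be positive, and one omission moves 43/110 = 39.1% to 42/110 = 38.2%. Zero against one suits at most the inhibitory subset; protocol 1.2.3 reports that no subject in CSL830_2001 developed inhibitory antibodies.

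**5. Effect on timing.** In the subject-based rate, time at risk stops at the first event. If an unscheduled positive is ignored and the next scheduled sample is positive, the event is dated up to 28 weeks late: 196/365.25 = 0.54 years, or 0.54/100.2 = 0.5% of the total. That is negligible for the denominator. Attribution is different: approach 1 in 4.7.1 keeps only events that start on the randomized dose, and approach 3 assigns events to the dose being taken. If a dose increase falls between the two samples, the event leaves approach 1 and moves to another dose in approach 3.

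**The case against.** **Measurements are not events.** Section 3.3.4 speaks of measurements, while 4.7.1 counts events and has no visit restriction. A reader might infer that the SAP removes unscheduled positives from the primary rate; the documents do not establish that. The primary rate is ambiguous, not shown to be wrong. The overall antibody table is different, because the rule and the table sit in the same section.

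**Findings reach the AE tables.** SAP 4.7.2.3 presents clinically significant abnormal laboratory data as AEs, and a DVT or PE confirmed after a raised score is an AESI and SAE (SAP 4.7.5). So it would be wrong to say that such findings vanish. But the antibody endpoint does not require clinical significance, and an AE entry does not put the subject back into the antibody count.

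**DVT/PE scores and seroconversion.** A reader might infer that the rule also removes raised scores and seroconversions from ever-occurring counts. It does not: SAP 4.7.5 summarizes scores only by visit, and 4.7.2.3 lists viral serology only, so the SAP has no such summary to distort. The fault there is separate: percentages in protocol 2.2.2 and 11.3.3.2 were not carried into the SAP.

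**Symptom-driven visits are not named.** The examples given for unscheduled visits are retraining, repeating a procedure and collecting medication. That stands. Protocol 10.3 permits clinically indicated extra testing but does not say how often it happens. Withdrawal assessments are entered as Week 53 or Week 88 visits, so they are not lost.

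**Nothing is concealed.** Unscheduled results are listed, and SAP 4.7.1 plans a by-subject listing of primary endpoint events. That helps a reader of listings and leaves the tables unchanged.

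**Conclusion.** The concern holds for anti-C1-INH antibodies. Applied as written, the rule omits from the overall antibody table any subject whose only positive came from an unscheduled sample. For the primary person-time rate the SAP leaves open whether that positive counts and which date it carries. The rule can therefore understate or delay antibody events.

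The size is unknown, since it depends on how many unscheduled antibody samples were taken and found positive. Under the assumptions above, one omitted subject is worth 0.9 percentage points of 110 subjects. The zero-or-one contrast, 0 against 0.010 per year at 100 person-years or 0 against 0.005 at 195, is illustrative and relevant mainly to inhibitory antibodies. The documents do not support a claim that confirmed thromboembolic events are undercounted.

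**What to change.** 1. In SAP 3.3.4 and 4.7.2.3, limit the exclusion of unscheduled results to by-visit descriptive tables and plots.
2. In SAP 4.7.2.3, state that unscheduled antibody results count in the overall antibody table. In 4.7.1, state that they count in the primary person-time antibody rate, with the date of the unscheduled sample as the event date.
3. Separately, either restore the protocol's percentages of subjects with increased DVT/PE scores and of subjects who become seropositive, or record their removal in SAP 4.14, whose unredacted text does not mention it. If restored, unscheduled results should count there too.

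Items 1 and 2 cost a few sentences of SAP text and a small programming change. Item 3, if the percentages are restored, adds a few tables. The results are already to be listed, so no new data are needed.
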